1.1.5.1.3. Subject Status and Time on Treatment

The median duration of treatment was 8.6 months (range 1.4 to 21.7 months) for all 33 subjects in Arms A and B. The median duration of treatment was 15.5 months (range 6.5 to 21.7 months) for the subjects with CR, PR, or CI, 15.5 months (range 14.0 to 21.7 months) for subjects with CR or PR, and 6.9 months (range 1.4 to 19.3 months) for subjects with stable disease. Subjects who did not have CR, PR, CI, or evidence and maintenance of clinical benefit (defined as \geq 50% improvement in leukocytosis, a \geq 50% improvement in thrombocytosis, a \geq 50% decrease in palpable splenomegaly, or a \geq 50% improvement in RBC transfusion requirement) were discontinued from treatment even if they did not meet criteria for progression. Of the 33 subjects, 25 (75.8%) discontinued treatment, 16 (48.5%) of whom discontinued due to insufficient response or the start of alternative therapy. Two (2) subjects progressed and 1 subject relapsed while on treatment. Two (2) subjects (6.1%) discontinued due to an adverse event. As of the cut-off date (December 2014) for this analysis, 8 subjects are still on treatment, 6 of them with ongoing CR, PR, or CI.

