Progressive Disease	Splenomegaly requires MRI showing a ≥25% increase in spleen volume from baseline or
	Appearance of a new splenomegaly that is palpable at least 5 cm below the LCM or
	A ≥100% increase in palpable distance, below LCM, for baseline splenomegaly of 5-10 cm or
	A 50% increase in palpable distance, below LCM, for baseline
	splenomegaly of >10 cm or Leukemic transformation confirmed by a bone marrow blast count of >20% or
	A peripheral blood blast content of $\geq 20\%$ associated with an
Stable Disease	absolute blast count of $\ge 1 \times 10^9/L$ that lasts for at least 2 weeks Belonging to none of the above listed response categories
Relapse	No longer meeting criteria for at least CI after achieving CR, PR, or
Relapse	CI, or
	Loss of anemia response persisting for at least 1 month or
	Loss of spleen response persisting for at least 1 month

Benefit must last 12 weeks. This applies to clinical improvement, anemia response, spleen response, and symptoms response.

Increase in severity of anemia constitutes the occurrence of new transfusion dependency or a ≥2.0 g/dL decrease in hemoglobin level from pretreatment baseline that lasts for at least 12 weeks. Increase in severity of thrombocytopenia or neutropenia is defined as a 2-grade decline, from pretreatment baseline, in platelet count or ANC, according to the Common Terminology Criteria for Adverse Events (CTCAE) Version 4.03. In addition, assignment to CI requires a minimum platelet count of ≥25,000 X 10⁹/L and ANC of ≥0.5 x 10⁹/L.

Transfusion dependency before study enrollment is defined as transfusions of at least 6 units of packed red blood cells (PRBC), in the 12 weeks prior to study enrollment, for a hemoglobin level of <8.5 g/dL, in the absence of bleeding or treatment-induced anemia. In addition, the most recent transfusion episode must have occurred in the 28 days prior to study enrollment. Response in transfusion-dependent patients requires absence of any PRBC transfusions during any consecutive "rolling" 12-week interval during the treatment phase, capped by a hemoglobin level of ≥8.5 g/dL.

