10.2. Discontinuation of Study Treatment

Investigators are encouraged to keep a subject experiencing clinical benefit in the study unless significant toxicity puts the subject at risk or routine noncompliance puts the study outcomes at risk. If a subject's study treatment must be discontinued before the end of the treatment regimen, then this will not result in automatic withdrawal of the subject from the study.

A subject's study treatment should be discontinued if:

- The investigator believes that for safety reasons (eg, adverse event) it is in the best interest of the subject to discontinue study treatment
- The subject becomes pregnant
- The subject experiences overt disease progression or relapse
- The subject experiences unacceptable toxicity
- The subject refuses further treatment
- A serious protocol violation has occurred, as determined by the principal investigator or the sponsor

End-of-treatment and posttreatment follow-up assessments should be obtained. The reason(s) a subject discontinues treatment will be recorded on the CRF.

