2.1.5. Other General Definitions

2.1.5.1. Individual Study Start/Treatment Start (Day 1), Study Day and Month

Individual Study Start /Treatment start is the date of the Cycle 1, Day 1. If study drug was not administered to a subject, study start is defined as the date of randomization.

The study day is equal to the date of the procedure minus the date of study start plus 1.

A month is defined as 365.25/12 days.

2.1.5.2. End of Treatment, End of Study, Time on Treatment , and Time on Study for Individual Subject

For each individual subject, disposition definitions are defined as below:

End of treatment is defined as the date of the last dose of the study drug. The end of Study is the date of death or the date last known to be alive, defined as the maximum date of the following study evaluations: randomization, vital signs, ECOG performance status, MRIs, physical examination, bone marrow evaluations, labs (hematology, chemistry), study drug administration, subsequent therapy, investigator-assessed PD, relapse from CR, investigator determined response, and survival follow-up.

The treatment cycle is defined as 21 days.

Time on treatment (in weeks) is equal to (the end date of treatment – the date of Cycle 1, Day 1 + 1)/7.

Time on study (in months) is equal to (the end date of follow-up – the date of Cycle 1, Day 1 + 1)/30.4375.

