2.3.8.1.4. Response Assessment Criteria

All assessments will be done according to the modified myeloproliferative neoplasms research and treatment (IWG-MRT) response criteria defined in the protocol ([Table 1](#), [Table 2](#)).

Table 1: Response Categories

Response Category	Required Criteria
	For all response categories, benefit must last for ≥ 12 weeks to qualify as a response
Clinical Improvement (CI)	The achievement of anemia, spleen or symptoms response without progressive disease or increase in severity of anemia, thrombocytopenia, or neutropenia ^a
Anemia Response	Subjects not transfusion dependent at baseline: a ≥ 20 g/dL increase in Hb ^b Transfusion dependent subjects at baseline: becoming transfusion independent. Transfusion independence is defined as absence of any pRBC transfusions for at least 12 “rolling” weeks ^b
Spleen Response	A baseline splenomegaly that is palpable at 5-10 cm, below the LCM, becomes not palpable or A baseline splenomegaly that is palpable at >10 cm, below the LCM, decreases by $\geq 50\%$ A spleen response requires confirmation by MRI showing $\geq 35\%$ spleen volume reduction
Symptoms Response	A $\geq 50\%$ reduction in the modified MFSAF v2.0 TSS ^c
Progressive Disease	Splenomegaly requires MRI showing a $\geq 25\%$ increase in spleen volume from baseline or Appearance of a new splenomegaly that is palpable at least 5 cm below the LCM or A $\geq 100\%$ increase in palpable distance, below LCM, for baseline splenomegaly of 5-10 cm or A 50% increase in palpable distance, below LCM, for baseline splenomegaly of >10 cm or Leukemic transformation confirmed by a bone marrow blast count of $\geq 20\%$ or A peripheral blood blast content of $\geq 20\%$ associated with an absolute blast count of $\geq 1 \times 10^9/L$ that lasts for at least 2 weeks
Stable Disease	Belonging to none of the above listed response categories
Relapse	No longer meeting criteria for at least CI after achieving CR, PR, or CI, or Loss of anemia response persisting for at least 1 month or Loss of spleen response persisting for at least 1 month

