2.3.8.1.5. Spleen and Response Assessment by Investigator

Spleen and response assessment will be performed locally by investigators based on radiological images and using the modified myeloproliferative neoplasms research and treatment (IWG-MRT) response criteria (Table 1, Table 2). In addition, tumor assessment of progressive disease (PD) can also be done based on clinical evidence other than radiological images, which is collected on the CRF.

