2.3.8.3.2. Duration of Response

Definition

Response endpoints include: CR/PR, CR/PR/CI, anemia response, spleen response, and symptom response per modified IWG-MRT criteria. For each of the response endpoints, duration of response will be calculated from the date of initial documentation of a response to the date of first documented evidence of PD or death, whichever occurs first, regardless of the use of subsequent anti-cancer therapy prior to PD or death. Subjects who are progression-free and alive, or have unknown status will be censored at the last disease assessment.

Analysis Methods

The Kaplan-Meier method will be used to descriptively summarize each duration of responses for responders: CR/PR, CR/PR/CI, Spleen, Anemia, and Symptom Response

per modified 2013 IWG-MRT criteria. Analyses based on IRC response and investigator response will be performed separately.

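### Every duration of response ends only at PD or death, so a response that is lost without PD keeps counting as response

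*SAP*

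**What the plan says.** SAP 2.3.8.3.2 gives one rule for five response endpoints. Each duration runs "from the date of initial documentation of a response to the date of first documented evidence of PD or death, whichever occurs first", whether or not another anti-cancer therapy was started in between. On censoring it says: "Subjects who are progression-free and alive, or have unknown status will be censored at the last disease assessment". Kaplan-Meier summaries in responders follow, separately for IRC and investigator response.

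SAP Table 1 (2.3.8.1.4) has separate rows for Progressive Disease and Relapse. Relapse means no longer qualifying for at least CI, or loss of the anemia response for at least 1 month, or "Loss of spleen response persisting for at least 1 month". Protocol Table 9 (9.2.1) has the same row, including "Loss of anemia response persisting for at least 1 month or" the spleen counterpart. The PD row covers spleen growth relative to baseline (volume or palpation), new splenomegaly, and leukemic transformation by marrow or blood blasts.

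Protocol 10.2 keeps the two ideas apart when it lists reasons to stop treatment: "The subject experiences overt disease progression or relapse". Protocol 11.4 names Kaplan-Meier for duration but gives no end event.

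**The concern.** A duration of response should stop when the response stops. Here a subject who returns to transfusion dependence, or whose symptom score returns to its baseline level, stays in response until PD, death or the last disease assessment. For subjects with an event, and within one assessment source, the anemia, spleen and symptom durations can differ only in their start dates, although Protocol 9.2.2 lists them as separate secondary endpoints.

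Duration of responses is a secondary objective, and SAP 1.2 says the development decision will rest on the totality of the data. If responses are lost before PD, what is labelled duration of response is time to PD or death among responders, and durability will tend to look better than it was.

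**Working it through.** The documents give no event count, power or expected value for duration of response, so there is no planned figure to reproduce.

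**1. Does PD stand in for loss of response? (SAP Table 1)**

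| Response | What loss looks like | Is that PD in itself? |
|---|---|---|
| Anemia | Hemoglobin falls back or transfusions resume | No; PD has no such criterion |
| Symptom | TSS reduction falls below 50% | No; PD has no such criterion |
| Spleen | Volume or palpable length regrows | Only if a PD threshold is also met |
| CR/PR, CR/PR/CI | Criteria no longer met | Only if a PD criterion is also met |

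**2. The spleen gap.** Response needs at least a 35% volume reduction, so volume is at most 65% of baseline. Volume PD needs at least a 25% increase from baseline, so at least 125%. Regrowth possible between the two is 125/65 - 1 = 92%. By palpation, a 16 cm baseline spleen responds at 8 cm or less (50% decrease) and reaches PD at 24 cm (50% increase), a threefold regrowth (24/8).

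**3. Direction.** For each subject, time to PD or death cannot be shorter than time to the earliest of loss, PD or death. A Kaplan-Meier estimate can still occasionally go the other way. Take three subjects: one loses response at month 1 and has PD at month 3, one is censored at 2, one has an event at 4. At month 3 the estimate is 2/3 = 0.67 if loss counts, and 1/2 = 0.50 under the SAP rule.

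**4. Size with constant hazards (assumed).** Let L be the hazard of loss and P the hazard of PD or death, with f = L/(L+P) the share of first failures that are loss of response. If loss counts, the median is ln2/(L+P); under the SAP rule it is ln2/P. The ratio is (L+P)/P = 1/(1-f): 1.00 at f = 0, 1.11 at 10%, 1.33 at 25%, 2.00 at 50%.

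**5. With the 12-week minimum.** A response must last 12 weeks, so m = 84/30.4375 = 2.76 months is free of events. With T the loss-inclusive median, the ratio is [m + (T-m)/(1-f)]/T.
- T = 14 months (the median in Protocol 1.1.5.1 for the earlier imetelstat study, whose end-event rule is not given): 1.09, 1.27, 1.80 at f = 10%, 25%, 50%.
- T = 6 months (assumed): 1.06, 1.18, 1.54.

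**6. Adding behavior after loss and the SAP censoring rule.** This is a simulation of 300,000 responders in each of 144 scenarios, all inputs assumed: T = 6 or 14; PD/death hazard 1, 2 or 4 times as high after loss; deaths 30% or 70% of that hazard; assessments ending 3 months after loss; deaths captured to cutoff and all others censored at the last assessment; cutoff 14-30 or 18-33 months after response. Ratios of Kaplan-Meier medians:

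| f | Ratio |
|---|---|
| 0 | 1.00 |
| 5% | 1.01-1.04 |
| 10% | 1.02-1.09 |
| 25% | 1.07-1.25 |
| 50% | 1.21-1.69 |

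**7. Effect of censoring alone.** At T = 14 and f = 50%, with 200,000 responders and cutoff 14-30 months, the SAP censoring rule lowers the ratio from 1.81 to 1.61 (hazard unchanged after loss, 70% deaths) but raises it from 1.31 to 1.42 (hazard 4 times as high, 30% deaths). At T = 6 it changes almost nothing.

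**The case against.** The strongest reply is that the rule is explicit, the endpoints are secondary and descriptive, no test or arm comparison depends on them, and a reader can see what was measured. All of that is true, and it limits the severity. It does not make time to PD or death a duration of response.

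Second, some losses will be caught. Under SAP 2.3.8.1.5, assessment of PD "can also be done based on clinical evidence other than radiological images", and a 5-10 cm baseline spleen that became non-palpable and returns at 5 cm or more could be read as new splenomegaly, which is PD. This narrows the spleen gap. It does not make relapse an end event, and Table 1's PD row still has nothing for loss of an anemia or symptom response.

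Third, the size rests wholly on assumptions, and at f = 10% it is small. The simulation also leaves out SAP 2.1.3, which cuts tabulated data at dose escalation for Arm B subjects who escalate. This stands.

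Four stronger readings are tempting and are not supported:
- That the SAP contradicts the protocol. Protocol 11.4 names no end event, so this is a gap in the SAP rule.
- That the earlier imetelstat study supplies f. Protocol 1.1.5.1.3 says "Two (2) subjects progressed and 1 subject relapsed while on treatment", but that counts all 33 subjects, does not say the two who progressed had responded, and omits deaths. One in three is not an estimate of f.
- That the censoring rule always adds to the overstatement. Step 7 shows that it can move the ratio either way.
- That SAP 2.1.5.2 treats relapse as an analysis event. Its list ("investigator-assessed PD, relapse from CR, investigator determined response, and survival follow-up") only names data sources for the last-known-alive date. Protocol 10.2 is the better evidence that relapse and progression are distinct.

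**Conclusion.** The point holds and should be fixed. Followed exactly, SAP 2.3.8.3.2 counts time after a lost response as response, and no other section of either document corrects this. The over-time summaries of TSS and spleen size in SAP 2.3.8.5 show group patterns but do not repair the duration estimate.

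The direction is upward in general, though not for every Kaplan-Meier estimate. The amount depends on how often response is lost before PD or death, which the documents do not state. It is nil if that never happens; the ranges in step 6 are illustrations under the assumptions listed there. The co-primary analyses and their type I error are untouched.

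**What to change.** Define each duration as ending at the earliest of loss of that response, PD or death, with loss dated at the first assessment that shows it:
- **Spleen and anemia:** use Table 1's Relapse lines (loss for at least 1 month), and state whether palpation, MRI or either establishes spleen loss.
- **CR/PR/CI:** no longer meeting at least CI.
- **CR/PR:** state whether falling to CI ends the response.
- **Symptom:** Table 1 has no symptom-loss line, so add one: TSS reduction below 50% with a stated persistence, and a rule joining the e-diary (to Week 48) to the Recall Form used afterwards. Two consecutive Recall Forms, 21 days apart with 7-day recall, span 21 + 7 = 28 days but cover only 14.
- **Unconfirmed loss:** state how it is handled, for example as an event at the first assessment showing it. This is needed on treatment too, because MRI is every 12 and later every 24 weeks and marrow every 24 weeks. After the End-of-Treatment visit the schedule has one MRI and one palpation at 3 months, if feasible, and no routine hematology.

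Keep the present definition as a supportive analysis labelled time to PD or death among responders.

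The cost is SAP wording, a separate loss derivation for each response, and the new symptom rule, on data largely already collected. Some losses will stay unconfirmed and depend on the stated rule. Reported durations will usually, though not always, be shorter.

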2.3.8.4. Overall Survival

Definition

Overall Survival is measured from the date of Cycle 1, Day 1 to the date of the subject's death. If the subject is alive or the vital status is unknown, OS will be censored at the date that the subject is last known to be alive.

Analysis Methods

The Kaplan-Meier method will be used to estimate the distribution of OS for each treatment arm. One- and two-year overall survival rates, based on Kaplan-Meier estimates, for the 2 treatment arms will be presented, along with their 95% confidence interval.

Analysis based on the ITT population will be the core analysis for OS analysis. In addition, the following analyses for overall survival will be performed:

- 1) Overall survival time with censoring at dose escalation for subjects who were in Arm B and subsequently dose escalated to 9.4 mg/kg
- 2) Overall survival time with Rank Preserving Structural Failure Time (RPSFT) Method and Overall survival time with Inverse Probability of Censoring Weighting (IPCW) Method
- 3) Overall survival time excluding subjects who were in Arm B and subsequently dose escalated to 9.4 mg/kg
- 4) Overall survival time excluding subjects who were enrolled on or after Sept 9, 2016, when at the time study enrollment was suspended. Those subjects who were already in screening phase and subsequently determined to be eligible for the study, were allowed to proceed with treatment assignment to the 9.4 mg/kg arm per investigator discretion, subject agreement, and IRB/IEC notification.

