- Beginning with Protocol Amendment 2, subjects in Arm B (4.7 mg/kg) may continue to receive their current imetelstat dose or have the dose increased to 9.4 mg/kg at the investigator's discretion and according to the guidance provided in Section 6. Dose escalation for these subjects may occur at any cycle of the Treatment Phase. Subjects who have their dose increased will have additional MRI and spleen assessments before receiving the first dose of imetelstat 9.4 mg/kg. Additional blood samples will be collected for biomarker assessments before and after the first dose of imetelstat 9.4 mg/kg, and blood samples for PK assessment will be collected after receiving the first dose of imetelstat 9.4 mg/kg.

TIME AND EVENTS SCHEDULE (EXTENSION PHASE)

Use this Time and Events Schedule after local IEC/IRB approval of Amendment 3.

Study Procedures	All Subjects	Extended Treatment (21-day treatment cycle)	Extended Follow-up (Every 16 weeks ± 7 days)
Informed consent	Xa		
Dispense/administer study drug		X (Day 1)	
Serious adverse event monitoring ^b		X^{b}	
Survival status			X ^c

a All subjects must provide informed consent to enter the Extension Phase. This must occur before the first dose of imetelstat for subjects continuing treatment in the Extension Phase.

Submit a Serious Adverse Event Form to the sponsor within 24 hours of awareness of the event for all serious adverse events. If the subject has a hemorrhagic serious adverse event, INR (or PT), aPTT, and platelet count will be assessed and reported in the serious adverse event report. If the subject experiences a hepatic serious adverse event, serum chemistry and an expanded liver panel will be assessed and reported; if the event includes Grade 3 or 4 ALP elevation, ALP fractionation or 5'neucleotidase will also be assessed and reported. Serious adverse events will be reported from the time the Extension Phase ICF is signed and dated until 30 days after the last dose of imetelstat.

c Assessment of survival status is required for all subjects who enter the Extension Phase, including those who discontinued treatment during the main study.

TIME AND EVENTS SCHEDULE (PK SAMPLING)

Study Day	PK Blood Sampling Time ^a	Serial (Intense) PK Blood Sampling ^b	Sparse PK Blood Sampling ^b	Sparse PK Blood Sampling Dose Escalation (4.7 to 9.4 mg/kg) ^e
Cycle 1, Day 1	0 (before start of infusion)	X		
Cycle 1, Day 1	1 h	X		
Cycle 1, Day 1	2 h ^c	X		
Cycle 1, Day 1	3h-5h	X		
Cycle 1, Day 1	6h-10h	X		

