6. DOSAGE AND ADMINISTRATION

Imetelstat Sodium (GRN163L) for Injection (imetelstat) is the investigational product in this study and will be provided by the sponsor. Imetelstat will be administered as a 2-hour IV infusion (\pm 10 minutes) at a constant rate using a programmable volumetric infusion pump. The baseline weight will be used to calculate the dose of imetelstat. The dose should be recalculated if there is a \geq 10% weight change from baseline. Subjects in Arm A will receive imetelstat 9.4 mg/kg every 3 weeks and subjects in Arm B will receive 4.7 mg/kg every 3 weeks. Subjects may receive treatment until disease progression or unacceptable toxicity. Study drug may be held for up to 21 days from the expected start date of the scheduled cycle; a hold >21 days must be reviewed and approved by the sponsor. Imetelstat should be discontinued permanently if it cannot be restarted within 21 days due to toxicity, unless approved by the sponsor. For treatment of hematologic toxicities, granulocyte colony stimulating factors (G-CSF) are permitted for neutropenia as well as blood transfusions for anemia or thrombocytopenia.

If a subject's status changes (including laboratory results or receipt of additional medical records) after screening but before the first dose of study drug is given such that he or she no longer meets all hematologic eligibility criteria, the decision to administer study drug on Cycle 1 Day 1 is at the discretion of the investigator provided that the subject does not meet any threshold for dose modification.

Dose Escalation Following Amendment 2

[figure not shown]
Beginning with Protocol Amendment 2, subjects in Arm B (4.7 mg/kg) may continue to receive their current dose of imetelstat or, at the discretion of the investigator, have their dose increased to 9.4 mg/kg. To be eligible for this dose escalation, a subject must meet study eligibility criteria for hematology laboratory values (inclusion criterion 8.1; ie, ANC \ge 1.5 x 10⁹/L; platelets \ge 75 x 10⁹/L) and biochemical laboratory values (inclusion criterion 9.1; ie, AST and ALT \le 2.5 x ULN, ALP \le 5 x ULN, serum creatinine \le 2 x ULN, total bilirubin \le 3 x ULN, direct bilirubin \le 2 x ULN). In addition, subjects may not meet any threshold for dose modification for hematologic toxicity

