(Section 6.1), non-hematologic toxicity (Section 6.2), or hepatic toxicity (Section 6.3). A subject who had a dose reduction at any time during the study is not permitted to dose escalate.

Treatment During the Extension Phase

Once the end of the main study has been reached, subjects who are receiving benefit from study treatment may continue to receive imetelstat during the Extension Phase. Dose modification guidelines provided in the following sections will continue in the Extension Phase. Subjects may receive treatment in the Extension Phase until there is loss of benefit or unacceptable toxicity, as determined by the investigator according to local standard of care.

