9. STUDY EVALUATIONS

9.1. Study Procedures

9.1.1. Overview

The Time and Events Schedules summarize the frequency and timing of efficacy, pharmacokinetic, immunogenicity, pharmacodynamic, biomarker, and safety measurements applicable to the main study and to the Extension Phase. As of Amendment 3, subjects will follow the Time and Events Schedule for the Extension Phase. Additional detail is provided in Section 9.1.5.

The total blood volume for the study is approximately 604 mL (Table 8).

Table 8: Volume of Blood to be Collected From Each Subject

	Volume per	No. of Samples	Total Volume of
Type of Sample	Sample (mL)	per Subject ^a	Blood (mL)b
Safety (including screening and posttreatment assessments)			
- Hematology including efficacy	5	19	95
- PT/INR and aPTT	5	15	75
- Serum chemistry and expanded liver panel ^c	10	20	200
- Hepatitis Serology ^d	13	1	13
- Serum β-hCG pregnancy tests	2	1	2
Pharmacokinetic samples (intensive or sparse) ^g	2	22	44
Immunogenicity	2	14	28
Pharmacodynamic samples ^f	14.5	6	87
Biomarkers (Mutation analysis) ^e	6	4	24
Peripheral blood for cytogenetics (if required)	4	5	20
Biomarkers (Immunophenotyping)	4	4	16
Approximate Total			604

- Volumes below derived for median 12 cycle duration and includes end of study visit.
- Calculated as number of samples multiplied by amount of blood per sample
 Serum chemistry includes basic liver function tests. An expanded panel of liver function tests is required at screening and may also be required for safety reasons.
- Includes 2.5 mL of blood for hepatitis PCR testing when required to confirm study eligibility.
- Samples will be collected every 12 weeks until disease progression.
- Four additional 14.5-mL blood samples (58 mL total) for pharmacodynamic analysis are required for subjects who have their dose increased from 4.7 mg/kg to 9.4 mg/kg.
 Up to 4 additional 2-mL blood samples (up to 8 mL total) for sparse PK analysis are required for subjects who have their
- dose increased from 4.7 mg/kg to 9.4 mg/kg; and up to two, 2-mL time-matched blood PK samples are required for subjects who have bone marrow aspirate collected for PK analysis at Weeks 24 and 48.

Note: An indwelling intravenous cannula may be used for blood sample collection.

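### SAP 2.3.8.4 item 3 drops Arm B subjects from Cycle 1 Day 1 because they escalated later, so this supplementary OS curve is expected, though not certain, to sit too low even with no dose effect

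*SAP*

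**What the plan says.** SAP 2.3.8.4 starts the survival clock at Cycle 1 Day 1 and plans Kaplan-Meier curves with one- and two-year rates for both arms. The main analysis is stated plainly: "Analysis based on the ITT population will be the core analysis for OS analysis". Four further analyses follow:

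- Item 1 censors Arm B subjects at escalation.
- Item 2 applies RPSFT and IPCW.
- Item 3 is "Overall survival time excluding subjects who were in Arm B and subsequently dose escalated to 9.4 mg/kg".
- Item 4 removes subjects enrolled from 9 September 2016.

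No landmark or time-dependent rule is attached to item 3.

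The conditions for escalation are in the Protocol. It became possible with Amendment 2. The dose-escalation footnote to the main Time and Events Schedule says "Dose escalation for these subjects may occur at any cycle of the Treatment Phase". Protocol section 6 leaves the choice to the site: a subject may, "at the discretion of the investigator, have their dose increased to 9.4 mg/kg". It also sets conditions: "To be eligible for this dose escalation, a subject must meet study eligibility criteria for hematology laboratory values", with the matching biochemistry limits and no current threshold for dose modification. Finally, "A subject who had a dose reduction at any time during the study is not permitted to dose escalate".

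**The concern.** Item 3 decides who is in the analysis at time zero by an event that happens later and that only survivors can experience. A subject who died or stopped drug before escalating always stays in. A subject who stayed alive, on drug and in adequate laboratory condition, and was then escalated, is removed together with all the time already survived. The person-time removed is selected to contain no deaths before escalation, so the remaining Arm B group looks worse without any effect of dose.

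Only Arm B loses subjects, and its curve would sit next to an untouched 9.4 mg/kg curve. SAP 2.3.8.1.1 plans no comparison between arms, but SAP 1.2 names survival among the inputs to the development decision. An uncaptioned item 3 curve invites the reading that it shows survival on 4.7 mg/kg alone, which it does not estimate.

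**Working it through.** The documents give no figure for item 3, so there is nothing to reproduce. All magnitudes below are illustrations under no dose effect.

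**1. Closed form, escalation unrelated to prognosis.** Let a share q of subjects alive at u months escalate at u, and let S be true survival. After u, the item 3 curve is

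S_excl(t) = S(t) × (1 − q) / (1 − q × S(u)).

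Since S(u) < 1, the multiplier is below 1.

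**2. Inputs for time on drug.** Only subjects still on treatment can escalate, so q is smaller than the share selected.

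- Protocol Table 8 uses a planning figure: "Volumes below derived for median 12 cycle duration and includes end of study visit". That is 12 × 21 = 252 days, or 252 / 30.4375 = 8.3 months.
- The earlier myelofibrosis study gives a similar value: "The median duration of treatment was 8.6 months (range 1.4 to 21.7 months) for all 33 subjects". Only 16 of those 33 had received a prior JAK inhibitor.
- Protocol 3.2.1 reports a median of 4 cycles at the first interim review, or 84 days = 2.8 months. Treatment was still ongoing, so this is a low-side figure.

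**3. Worked example (assumed).** Exponential OS with median 20 months; u = 6 months, the average time since entry if entry was spread evenly over 12 months; 40% of those alive and on drug escalate.

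S(6) = 0.812, S(12) = 0.660, S(24) = 0.435.

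| Median time on drug | Share on drug at 6 months | q | Multiplier | 12-month OS | 24-month OS |
|---|---|---|---|---|---|
| 8.3 months | 2^(−6/8.3) = 0.606 | 0.4 × 0.606 = 0.242 | 0.758 / (1 − 0.242 × 0.812) = 0.943 | 66.0% → 62.2% | 43.5% → 41.1% |
| 2.8 months | 2^(−6/2.8) = 0.226 | 0.4 × 0.226 = 0.091 | 0.909 / (1 − 0.091 × 0.812) = 0.982 | 66.0% → 64.8% | 43.5% → 42.7% |

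After u the multiplier is constant, so the absolute fall is larger at one year than at two. In an arm of 40, the first row removes 40 × 0.242 × 0.812 ≈ 8 subjects. Simulating this case with staggered entry and escalation within 2 months gives 43.5% → 41.2% and an event-rate ratio (item 3 to all of Arm B) of 1.08.

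**4. Range over assumptions.** A simulation used 400,000 subjects in each of 288 scenarios: median OS 6, 12, 20 or 30 months; 20, 40, 60 or 75% of those alive and on drug selected; escalation spread over 0–2 or 0–18 months; median time on drug 6, 8.3 or 12 months; three selection patterns. Entry ran over the 12 months before the amendment, with cutoff 18 months after it. Results at 8.3 months on drug:

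| Who escalates | Event-rate ratio | Change in 24-month OS (points) |
|---|---|---|
| At random | 1.02 to 1.21 | −5.4 to −0.3 |
| Healthier subjects more often | 1.06 to 1.36 | −9.0 to −1.5 |
| Poorer-prognosis subjects more often | 0.98 to 1.16 | −3.2 to +0.8 |

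The ratio fell below 1 in 10 of the 288 scenarios, all with poorer-prognosis escalators. With 2.8–4 months on drug and random escalation, the ratio is 1.00 to 1.10 and the 24-month change −2.3 to −0.1 points. At one year, random escalation with 6–12 months on drug gives −11.6 to −0.6 points.

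**5. Sampling error.** For 40 subjects and 24-month OS of 0.435, the binomial standard error is √(0.435 × 0.565 / 40) = 0.078. Simulation with censoring gives 0.084.

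**6. Item 1 under the same 288 scenarios.** Change in 24-month OS: none if escalation is random; −4.5 to −0.3 points if healthier subjects escalate; +0.2 to +4.5 if poorer-prognosis subjects do. In the poorer-prognosis scenarios item 1 was further off than item 3 in 70 of 96. Under the other two patterns item 3 was worse.

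**The case against.** The strongest reply is that little depends on item 3. It is one of several descriptive additions to a core ITT analysis, no arm comparison is planned, and nothing in the SAP calls it survival on 4.7 mg/kg alone. The 24-month shift is often smaller than sampling error, and smaller still if the short time on drug at the first interim review is representative. All of this stands and limits the point. It does not remove it: the bias has an expected direction, and the confidence interval around the curve does not show it.

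A second reply is that the alternatives are not clean. This also stands. Item 1 can be biased in either direction by up to 4.5 points in these scenarios if escalation depends on prognosis. RPSFT rests on randomization, while SAP 1.5 and Protocol section 5 let subjects in screening be assigned directly to 9.4 mg/kg. IPCW weights may be unstable in a small arm.

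A reader might infer that the Arm B curve must be too low. The documents do not support certainty. Escalation was discretionary, and if poorer-prognosis subjects were escalated the shift can vanish or slightly reverse. A reader might also infer that the trial's survival result is compromised. It is not: item 3 leaves core ITT OS unchanged.

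**Conclusion.** Item 3 selects subjects from time zero on a later event that requires survival. With no dose effect it is expected, though not certain, to understate Arm B survival. The size for this trial cannot be computed: the number and timing of escalations, survival, time on treatment and final Arm B size are not given. The 40 treated Arm B subjects in Protocol 3.2.1 are a first-interim count. The illustrations rest on assumed survival, entry pattern, time on drug and selection. Within them, the two-year shift runs from negligible to several points and is often below one standard error; the one-year shift may be larger. No primary or safety conclusion depends on item 3. It merits correction because survival feeds the development decision and the correction is cheap.

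Two wording points in the same area are separate and minor; they add nothing to the weight of this one:

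- **SAP 2.1.3** sends post-escalation data to listings only, with no exception for survival. Read literally, core Arm B OS would become item 1. SAP 2.3.8.4 implies otherwise, because item 1 is additional to the core and RPSFT needs post-escalation survival.
- **The ITT set** is defined by randomization in both SAP 2.1.4.2 and Protocol 11.1. SAP 2.3.1 summarizes by randomized or registered arm, and item 4 presupposes that directly assigned 9.4 mg/kg subjects are in core OS.

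**What to change.** Delete item 3, or keep it under the label: selected on a post-baseline event; does not estimate OS on 4.7 mg/kg alone.

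For survival without escalation:

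- Present item 1 with the stated assumption that escalation is unrelated to prognosis, noting that it can be biased in either direction if not.
- Present IPCW with a caution about unstable weights in a small arm.
- Restrict RPSFT to randomized subjects.

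Separate clarifications:

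- Add to SAP 2.1.3 that the listings-only rule does not apply to core OS, RPSFT or item 4. Item 4 keeps the Arm B escalators and needs their later survival. IPCW censors at escalation and needs no exception.
- State whether directly assigned 9.4 mg/kg subjects are in the core OS set. If they are, record this as a departure from the randomized ITT definition in both SAP 2.1.4.2 and Protocol 11.1.

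The cost is a few sentences in the SAP, a note on the departure from the Protocol definition if it applies, and at most one supplementary table. No new data are needed.
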